14. Medical history of mental diseases of the patient or their parent(s)/adoptive parents.
15. Participation in other clinical trials for 3 months prior to enrollment in this study.
16. Patient's parents/adopters who are related to any of the on-site research personnel directly involved in the study or are an immediate relative of the investigator. 'Immediate relative' means husband, wife, parent, son, daughter, brother, or sister (regardless of whether they are natural or adopted).
17. The patient's parent/adopter who works for OOO "NPF "MATERIA MEDICA HOLDING" (i.e. the company's employees, temporary contract workers, designated officials responsible for carrying out the research or any immediate relatives of the aforementioned).

Criteria for Withdrawal or Termination

1. Screening failure.

2. Failure or refusal of the patient to follow the protocol.
3. The necessity to use medications not permitted in the study.
4. An adverse event requiring discontinuation of the study drug.
5. Patient's or his/her parent's/adopter's decision to withdraw early for lack of efficacy or other reasons.
6. Pregnancy.
7. Cases not stipulated in the protocol where the investigator decides that further participation may harm the patient.
8. Eligibility error.

Number of patients

It is planned to include 400 patients, 360 of them will be randomized which is expected to yield at least 200 patients (100 per Raphamin and Placebo groups) completing all the protocol procedures.

Interim analysis

The protocol does not schedule unblinded interim analyses. At the sponsor's decision, blinded interim analysis may be carried out to specify population parameters and potential further specification of sample size (increase only).

Treatment

Group I

Name of the medicinal product: Raphamin

Active ingredient: affinity purified antibodies to human interferon-gamma – 10 000 UMA*,
affinity purified antibodies to CD4 – 10 000 UMA,
affinity purified antibodies to β 2-microglobulin major histocompatibility complex class I – 10 000 UMA,
affinity purified antibodies to β 1-domain of major histocompatibility complex class II – 10 000 UMA

* UMA – Units of Modifying Activity.

Excipients: lactose monohydrate, microcrystalline cellulose, magnesium stearate.

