Schedule of study procedures

Procedure/Visit	Visit 1 (Day 1)	Visit 2 (Day 5±1)	Visit 3 (Day 7±1)	Visit 4 (Day 14±1)
Informed consent	+			
Registration of a study patient in the IVRS* and assignment of patient ID	+			
Complaints collection	+	+	+	
Medical history	+			
Concomitant diseases and conditions	+	+	+	+
Physical examination	+	+	+	
ARVI symptoms	+	+	+	
Concomitant therapy	+	+	+	+
SARS-CoV-2 rapid test	+			
Pregnancy test	+			
Inclusion/exclusion criteria	+			
Randomization	+			
Nasopharyngeal swabs for PCR	+			
Safety laboratory tests**	+		+	

Procedure/Visit	Visit 1 (Day 1)	Visit 2 (Day 5±1)	Visit 3 (Day 7±1)	Visit 4 (Day 14±1)
Study drug supply	+			
Antipyretic drug supply	+			
Evaluation of the study drug safety	+	+	+	+
Patient diary	+	+	+	+
Study drug accountability and return			+	
Treatment compliance			+	
Visit completion	+	+	+	+
Telephone survey				+
Study completion***				+

* Interactive voice/web response randomization system
 ** Laboratory tests include hematology, urinalysis, serum chemistry (total protein, C-reactive protein, glucose, total bilirubin, creatinine, ALT, AST, cholesterol). Performed with availability of signed PIS and ICF including the patient's consent for blood and urine sampling.
 *** In case of early withdrawal the procedure may be carried out at Visits 1, 2 or 3.

Statistical Analyses

SAS-[9.4].⁵ will be used for data processing and statistical calculations.

Samples

Total set: all enrolled patients who have signed ICF. This sample will consider all the recorded AEs, including those occurred prior to the study therapy.

Safety population: all included and randomized patients who received at least one dose of the study drug. This sample will be used for **analysis of the study treatment safety and tolerability**, as all adverse events identified after the study drug administration will be recorded.

Full Analysis Set. This sample includes all enrolled patients, except for those who met at least one of the following events:

- 1) non-compliance with inclusion / exclusion criteria;
- 2) patient did not take a single dose of the study drug;
- 3) lack of any data about the patient after administration of the study drug.

This sample, the most consistent with the “Intention-to-treat” principle, will be used for the **Intention-to-treat analysis (ITT analysis)** of the study therapy efficacy.

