⁹ This rate is composite: 10% patients will be screening failures or discontinue the study for other reasons specified in the relevant protocol section, in 44.4% remaining patients the diagnosis will not be confirmed by PCR. The rate was assessed based on PCR findings obtained in "Multicenter double-blind placebo-controlled randomized parallel-group study of efficacy and safety of MMH-407 in the treatment of acute respiratory viral infection" (MMH-407-001).

various reasons, at least **400** patients will be required to sign informed consent, with **200** subjects per group.

Statistical criteria

All the statistical calculations will be performed using two groups of statistical criteria:

- parametric – to obtain effective evaluations for parameters of random values, if the relevant conditions of applicability of methods/models are not violated (e.g. sphericity, normality, proportionality of risks, etc.);
- non-parametric – in any other cases.

Parametric criteria

The application of parametric criteria will be accompanied by a check of models for applicability (e.g. Kolmogorov-Smirnov test, Shapiro-Wilk test, etc.).

The following parametric tests and approaches are to be used:

1. To evaluate the differences of continuous variables obtained in one group at two different visits – Student's test for matched samples.
2. To evaluate the temporal dynamics of the compared indicators – analysis of variance (ANOVA) or covariance (ANCOVA) in the modification with repeated measures.
3. In case of multiple comparisons between the groups will apply a variety of corrections for multiplicity (Dunnett, Tukey, Scheffe, Holm adaptive test), etc.
4. In case of abnormal data distribution, approaches with the Generalized Linear Models and / or Mixed Linear Models will be used.
5. Selection of the type of distribution, specification of the factor and covariance structures of the model will be made using fit-statistics such as AIC¹⁰ (Akaike information criterion).

To perform the above-mentioned statistical tests and techniques, it is assumed that the following SAS procedures are used:

- UNIVARIATE – check for normality of the compared distributions;
- CORR, MEANS – calculation of descriptive statistics;
- TTEST – Student t-test with all the modifications;
- GLM – analysis of General Linear Models for studying temporal dynamics (ANOVA, ANCOVA);
- GENMOD – analysis of Generalized Linear Models;
- MIXED – analysis of Mixed Linear Models.

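### Change over time is assigned to repeated-measures ANOVA in PROC GLM, with mixed models reserved for non-normal data, so patients with partial vital-sign records are likely to be dropped

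*Combined protocol and SAP*

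**What the plan says.** Under Statistical criteria, Parametric criteria, item 2 assigns the course of the compared indicators over time to "analysis of variance (ANOVA) or covariance (ANCOVA) in the modification with repeated measures". The SAS list that follows ties this to GLM, described as "analysis of General Linear Models for studying temporal dynamics (ANOVA, ANCOVA". The list is introduced with the words "it is assumed that the following SAS procedures are used". The opening of Statistical criteria names sphericity, with normality and proportional risks, among the conditions for using parametric methods.

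Mixed models appear in three places. Item 4 gives the trigger: "In case of abnormal data distribution, approaches with the Generalized Linear Models and / or Mixed Linear Models will be used". Item 5 adds that "specification of the factor and covariance structures of the model will be made using fit-statistics such as AIC". The SAS list includes "MIXED – analysis of Mixed Linear Models". The Non-parametric criteria offer the Friedman test for change over time.

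Under Samples, the Safety population is every randomized patient with at least one dose. The Full Analysis Set removes a dosed, eligible patient on data grounds only for "lack of any data about the patient after administration of the study drug". Criteria for Withdrawal or Termination allow a patient to leave because of an adverse event (item 4) or by a "decision to withdraw early for lack of efficacy or other reasons" (item 5).

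No section says how missing repeated measurements are handled. Footnote 6, under Evaluation of sample size, covers only whether a patient with gaps in the primary endpoint data may enter the per-protocol set.

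**The concern.** Classical repeated-measures ANOVA needs a complete row of measurements for each patient. With the REPEATED statement, GLM reads one row per patient and leaves out any row with a missing time point. This is general knowledge of the procedure and is not stated in the documents. Followed as written, roughly normal data with gaps go to GLM, and the analysis becomes one of patients with complete records, whatever population is named in the table title.

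The plan does list the tool that avoids this, but calls on it for the wrong reason. Non-normality does not justify a linear mixed model, which keeps the normal-error assumption. Incomplete follow-up does justify it, and the plan never mentions that as a trigger.

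At stake is the safety reading of vital signs. Patients may leave because of an adverse event, so those with incomplete records need not resemble the rest, and their recorded values would not be used.

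**Working it through.** **1. The plan's own figure.** The sample size uses a difference of 1 day, SD 2.5 days, two-sided alpha 0.05 and 80% power. Per group, n = (1.96 + 0.84)² × 2 × 2.5² / 1² ≈ 98.1, rounded up to 99, or 198 in total against the stated 200. Inflation gives 200 / (1 − 0.5) = 400. The figure reproduces. It rests on mean time to resolution, so nothing below changes it.

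**2. Which outcomes use the method.** Set against the Endpoints and Safety assessment lists:

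- Primary: a time to event. Not a repeated-measures comparison.
- Secondary efficacy: one AUC per patient, percentages, a time to event and an antipyretic count. None is assigned to repeated-measures ANOVA.
- Safety item 2: change in vital signs on treatment. This is the only listed outcome worded as change over time, and it belongs to the Safety population.
- Daily symptom and temperature scores: collected in the diary, but listed only as inputs to other endpoints. Whether they count as compared indicators in item 2 is left open.

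**3. Which form of GLM.** The text does not mention the REPEATED statement or the data layout. Two things point to the REPEATED form: item 2 asks for the repeated-measures modification, and sphericity is a named condition. Sphericity is the assumption of classical repeated-measures ANOVA, and GLM tests it through that statement.

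**4. How many patients could be lost.** The documents give no rate of missing follow-up readings. The composite withdrawal rate does not supply one: 400 × 0.9 = 360 uses up the 10% before randomization, and 360 × (1 − 0.444) ≈ 200 is PCR confirmation. The rates below are therefore assumptions, with gaps taken as independent between visits. I also assume that vital signs are taken at the physical examinations on Visits 2 and 3, that Visit 1 is complete, and that all 360 randomized patients are dosed.

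Share deleted = 1 − (1 − p)²; share with exactly one follow-up reading = 2p(1 − p); share with none = p².

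| p per visit (assumed) | Deleted by GLM | Of 360 | One reading | No reading |
|---|---|---|---|---|
| 2% | 1 − 0.98² = 4.0% | 14 | 3.92% | 0.04% |
| 5% | 1 − 0.95² = 9.8% | 35 | 9.5% | 0.25% |

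A mixed model with baseline as a covariate uses the patients with one reading, which is nearly all of those deleted in this illustration. It cannot use a patient with no follow-up reading, such as one who leaves before Visit 2 without a further examination.

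**5. Only if diary temperature were also analysed over time.** With 12 readings (six days, morning and evening), the share deleted is 1 − (1 − p)¹². At assumed p of 1%, 2% or 5%, this is 41, 78 or 165 of 360 patients. The plan does not list this analysis.

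**The case against.** The strongest reply is that this is a general menu of methods. The procedure list is only assumed, GLM on one row per visit drops just the missing rows, PROC MIXED is listed, and choosing covariance structures by AIC shows that mixed modelling is foreseen. Parametric methods also apply only if their conditions hold, so data that fail them go to the item 4 models or the Friedman test.

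Part of this stands: deletion of whole patients is likely under the wording but not certain. The rest does not remove the defect. Each of these exits depends on the distribution of the data or on model fit, and none on missing values. Approximately normal readings with gaps still go to GLM. In its standard form the Friedman test compares time points, not treatment arms.

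Two stronger readings are tempting and are not supported:

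- A reader might infer that the ITT efficacy analysis discards early leavers whom the Full Analysis Set keeps. That needs an efficacy outcome analysed by repeated measures, and none is listed. Vital signs belong to the Safety population.
- A reader might infer that the treatment effect is biased toward zero because poor responders leave placebo more often. The effect on daily scores, their variances and the link between symptoms and dropout would all have to be assumed, for an analysis that the plan does not contain.

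**Conclusion.** The point holds within a limited scope. The plan names an inferior method for change over time, reserves the better one for the wrong situation, and has no rule for gaps. In its usual form, the named method would turn the vital-sign analysis into one of complete cases, although the Safety population keeps every dosed patient. The same would apply to symptom or temperature scores only if they too were analysed over time.

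The conclusion rests on the usual behaviour of GLM with REPEATED and on reading item 2 with the sphericity condition as pointing to that form. The loss of 4.0% to 9.8% is an illustration under assumed rates. This should be corrected, but it does not threaten the trial's main efficacy conclusion.

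**What to change.** In Parametric criteria:

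- State which outcomes are analysed as change over time and in which population.
- Replace repeated-measures GLM in item 2 with a likelihood-based mixed model for repeated measures (PROC MIXED) on all available values. Include treatment, visit, treatment-by-visit and baseline value, with covariance unstructured or chosen by AIC as item 5 already allows.
- Remove non-normality as the trigger for linear mixed models in item 4. For non-normal responses, specify a likelihood-based generalized mixed model. Unweighted GEE in GENMOD is not an equivalent substitute, because it generally needs data missing completely at random.

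The cost is a change of wording, plus one added procedure if a generalized mixed model is needed, since the listed procedures do not clearly cover one. The result will rely on missing at random, which is weaker than what the complete-case analysis needs but still cannot be tested from the data. No sample-size figure changes.
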